7.9 Study size and feasibility

The PALOMA-2 trial target sample size was 650 patients with 1:1 randomization. This sample size was based on 90% power to detect a hazard ratio for progression of 0.69 at a one-sided alpha level of 0.025 (assuming 347 events).² A total of 666 patients were included in the trial.

Sample size requirements to detect a range of hazard ratios relevant to the PALOMA-2 trial are presented in [Table 13](#). If the unweighted study sample size falls below the lowest estimate, corresponding to the required sample size to detect the point estimate for the hazards of progression or death observed in the trial with 80% power, implementation will pause. The study team and CARE Steering Committee will then consider the value of continuing the study with potentially insufficient power, given the lower primacy of statistical significance in an emulation setting.

Table 13. Sample size requirements

	Power	Hazard ratio for death	Ratio of exposed to unexposed	Alpha	Prevalence of death among the unexposed ^a	Total sample size required ^b
Trial sample size calculation, point estimate	90%	0.69	1:1	5%	57.7%	530
Trial sample size calculation, point estimate	80%	0.69	1:1	5%	57.7%	396
Trial result, upper confidence limit	90%	0.72	1:1	5%	57.7%	675
Trial result, upper confidence limit	80%	0.72	1:1	5%	57.7%	505
Trial result, point estimate	90%	0.58	1:1	5%	57.7%	246
Trial result, point estimate	80%	0.58	1:1	5%	57.7%	184

^a As reported in the trial.

^b Calculated using the *powerSurvEpi* R package²⁴, based on the sample size formula for proportional hazards modeling derived by Latouche et al.²⁵

In feasibility analyses ([Appendix B](#)) among adult, postmenopausal females with metastatic breast cancer and no evidence of ECOG performance status ≥ 2 in the data source, there were 944 individuals with evidence of initiating both palbociclib and letrozole, and 660 individuals who initiated letrozole only. This real-world study will include data for all individuals meeting study inclusion and exclusion criteria.

8. Strengths and Limitations

This emulation study is limited by several inherent differences between trial settings and non-interventional studies leveraging RWD.

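### Table 13 labels 57.7% as the event proportion in the unexposed, but all six totals, including the 184-patient pause threshold, use it for the whole sample

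*Combined protocol and SAP*

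**What the plan says.** Section 7.9, Table 13, lists six sample sizes: 530, 396, 675, 505, 246 and 184. They cover hazard ratios of 0.69, 0.72 and 0.58, each at 90% and 80% power, with 5% alpha and a 1:1 ratio. Every row carries 57.7% under the header "Prevalence of death among the unexposed". Its only source is footnote a: "As reported in the trial". No pooled or arm-level event count from the trial appears anywhere.

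The lowest total is a decision rule. "If the unweighted study sample size falls below the lowest estimate", implementation pauses, and that estimate is described as the size needed to detect "the point estimate for the hazards of progression or death observed in the trial with 80% power". The study team and Steering Committee then decide whether to go on, given the "lower primacy of statistical significance in an emulation setting".

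On the trial itself, Section 7.9 states: "The PALOMA-2 trial target sample size was 650 patients with 1:1 randomization". It gives the design basis as "90% power to detect a hazard ratio for progression of 0.69 at a one-sided alpha level of 0.025 (assuming 347 events"). Appendix B lists the trial sample as 444 treated and 222 comparator patients.

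**The concern.** A proportional-hazards sample size is the required number of events divided by the proportion of the whole sample expected to have one. If a comparator-arm proportion is used as that divisor when the treatment is assumed to work, events are overstated and the sample size is too small. The header says that 57.7% is a comparator-arm figure, and the totals treat it as a whole-sample figure.

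At stake is whether the powers in Table 13 are what they are said to be, and in particular whether 184 patients give the 80% power on which the pause rule rests.

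Two labelling slips sit beside this. The column headers refer to death, while the text and the endpoint concern progression or death. The text also says the trial was randomized 1:1, while Appendix B shows 2:1. The second slip bears on the main point: a proportion pooled over a 2:1 trial does not carry over unchanged to a 1:1 sample.

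**Working it through.** **Inputs.** Hazard ratios, powers, 5% alpha, 1:1 ratio, 57.7% and the six totals come from Table 13. The design figures (0.69, 90%, one-sided 0.025, 347 events) and the feasibility counts (944 and 660) come from the text of Section 7.9. The trial arm sizes (444 and 222) come from Appendix B.

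**Formula.** Events D = (z₀.₉₇₅ + z_power)² / [p(1−p) ln(HR)²], and N = D/ψ, where p is the exposed share and ψ is the event proportion of the whole sample. Two-sided 5% alpha is used; one-sided 5% does not reproduce the table.

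**Step 1: reproduce Table 13** with p = 0.5 and ψ = 0.577.

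| HR | Power | D | D/0.577 | Rounded up | Table 13 |
|---|---|---|---|---|---|
| 0.69 | 90% | 305.25 | 529.03 | 530 | 530 |
| 0.69 | 80% | 228.02 | 395.18 | 396 | 396 |
| 0.72 | 90% | 389.47 | 674.99 | 675 | 675 |
| 0.72 | 80% | 290.93 | 504.21 | 505 | 505 |
| 0.58 | 90% | 141.64 | 245.48 | 246 | 246 |
| 0.58 | 80% | 105.81 | 183.37 | 184 | 184 |

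All six match to the patient, so 57.7% was applied to exposed and unexposed patients together.

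**Step 2: suppose the header is right.** The unexposed proportion is 0.577 and the exposed proportion follows from the hazard ratio. Two assumptions bracket it:

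- Equal follow-up: exposed = 1 − 0.423^HR.
- Exponential event and censoring times: exposed = HR / (HR + 0.423/0.577).

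At 1:1, ψ is the mean of the two group proportions.

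| HR | Power | Stated N | ψ (equal / exponential) | N needed | Power at stated N |
|---|---|---|---|---|---|
| 0.69 | 90% | 530 | 0.512 / 0.531 | 596 / 575 | 86.4 / 87.5% |
| 0.69 | 80% | 396 | 0.512 / 0.531 | 446 / 430 | 75.3 / 76.7% |
| 0.72 | 90% | 675 | 0.519 / 0.536 | 750 / 727 | 86.8 / 87.8% |
| 0.72 | 80% | 505 | 0.519 / 0.536 | 561 / 543 | 75.8 / 77.1% |
| 0.58 | 90% | 246 | 0.485 / 0.509 | 293 / 279 | 84.5 / 86.2% |
| 0.58 | 80% | 184 | 0.485 / 0.509 | 219 / 208 | 73.0 / 75.1% |

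Totals rise by about 8–19%. In the threshold row, 184 patients give 184 × 0.485 ≈ 89 to 184 × 0.509 ≈ 94 events, against the 105.8 needed.

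**Step 3: suppose 57.7% is pooled.**

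- Pooled, and carried over unchanged to 1:1: 184 patients give 80.1% power. The totals stand and only the header is wrong.
- Pooled over 444:222 at HR 0.58: the arm proportions are 70.9% and 51.1% (equal follow-up) or 66.4% and 53.4% (exponential). At 1:1, ψ is 0.610 or 0.599, so 174 or 177 patients suffice and 184 gives about 82%.

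**Step 4: the stated trial allocation.** At HR 0.69 and one-sided 0.025, 90% power needs 305.3 events at 1:1 and 343.4 at 2:1. The stated 347 events give 93.3% at 1:1 and 90.3% at 2:1. The section's own design figures therefore fit 2:1, as does 444 + 222 = 666, the trial total it reports.

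**Step 5: unequal groups.** At the feasibility split (p = 944/1,604 = 0.5885), the threshold row needs 109.2 events. If the header is right, that is 220–234 patients, and 184 gives 70–73%. If 57.7% is pooled, it is 185–190 patients, and 184 gives 79–80%. The final split is unknown.

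**The case against.** The strongest reply is that nothing practical turns on this. Table 13 does not fix recruitment, because all eligible patients enter. The feasibility count is "there were 944 individuals with evidence of initiating both palbociclib and letrozole, and 660 individuals who initiated letrozole only", or 1,604 in all. The choice between 184 and 219 matters only after attrition of 86.3% (1 − 219/1,604) to 88.5% (1 − 184/1,604). A pause then leads only to discussion, and Section 5 judges agreement by direction and magnitude, not significance. This stands and limits the weight of the point. It does not remove it: the count was taken before all criteria were applied, Appendix B expects further attrition, and the rule exists for that case.

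A second reply is that a hazard ratio below 1 forces a lower whole-sample proportion only if censoring is similar in the two groups, and heavier censoring of comparator patients could offset the difference. This does not rescue the table. One unexposed proportion under one censoring pattern cannot give the same pooled 57.7% at hazard ratios of 0.58, 0.69 and 0.72.

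A third reply is that the header may correctly describe a comparator figure that was knowingly used for both groups as a simplification. The documents do not say so, and the stated powers would still be too high.

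It is fair to add that any replacement threshold depends on an assumption. Multiplying the proportion itself by the hazard ratio, a cruder device, would give 233 in place of 208–219.

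**Conclusion.** The mismatch is certain; its direction is not. Either the header is wrong and the 1:1 totals are adequate, or the header is right and all six totals are too small for their stated power. In the second case the 80% behind the pause rule is really 73–75% at 1:1. The range reflects the two follow-up assumptions in Step 2. No figure here allows for variance inflation from the weighting, for which the documents give no value. The 1:1 statement about the trial contradicts Appendix B and the section's own design events, and it affects how a pooled 57.7% should be carried into the table. The consequence for the study is probably small, but a stated decision threshold should have the power claimed for it.

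**What to change.** Check the trial report for what 57.7% is.

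- If it is the comparator-arm figure, recompute all six totals with the whole-sample proportion implied by each hazard ratio at the assumed allocation. State the assumption used and restate the pause threshold (about 208–219 at 1:1 under the assumptions above).
- If it is pooled, correct the header to say so and note the allocation over which it was pooled.

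In either case, relabel the death columns as progression or death, and reconcile the 1:1 description of the trial with 444 versus 222 and with the 347 design events.

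The cost is one look at the source, then either one header with a note or six figures and one threshold. No extra patients are needed and the analysis does not change.

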Appendix A: List of abbreviations

Abbreviation	Definition
ASD	Absolute standardized difference
CARE	Coalition to Advance Real-World Evidence through Randomized Controlled Trial Emulation
CDK4/6	Cyclin-dependent kinase 4/6
CNS	Central nervous system
CONSORT	Consolidated Standards of Reporting Trials
CTCAE	Common Terminology Criteria for Adverse Events
CYP3A4	Cytochrome P450 3A4
DBC	Database connection
ECG	Electrocardiogram
ECOG	Eastern Cooperative Oncology Group
EHR	Electronic health record
ER+	Estrogen receptor-positive
ERBB2	V-erb-b2 avian erythroblastic leukemia viral oncogene homolog 2
FDA	Food and Drug Administration
HER2-	Human epidermal growth factor receptor 2-negative
IPTW	Inverse probability of treatment weighting
NCI	National Cancer Institute
NLP	Natural Language Processing
OMOP	Observational Medical Outcomes Partnership

Abbreviation	Definition
PD-0332991	Palbociclib
PFS	Progression-free survival
PS	Propensity score
QTc	Heart-rate corrected QT interval
RCT	Randomized controlled trials
RECIST	Response Evaluation Criteria in Solid Tumours
RWD	Real-world data
RWE	Real-world evidence
rwPFS	Real-world progression-free survival
TdP	Torsade de Pointes
U.S.	United States

Appendix B: Preliminary feasibility assessment

STEP 1: STATE RESEARCH AIM, QUESTION, AND OBJECTIVES					
STEP 1a: Overarching research aim					
To emulate the PALOMA-2 randomized controlled trial of letrozole + palbociclib as first-line treatment in postmenopausal women with estrogen receptor-positive/human epidermal growth factor receptor 2-negative advanced breast cancer using real-world data.					
STEP 1b: Trial research question					
Among adult postmenopausal women with estrogen receptor-positive/human epidermal growth factor receptor 2-negative advanced breast cancer, does initial treatment with letrozole + palbociclib compared with treatment with letrozole alone result in longer progression-free survival?					
STEP 1c: Trial primary objective(s)					
Among adult postmenopausal women with estrogen receptor-positive/human epidermal growth factor receptor 2-negative advanced breast cancer, compare progression-free survival for patients treated with palbociclib and letrozole and patients treated with letrozole alone.					
DESIGN ELEMENTS	STEP 2: DESCRIBE ORIGINAL CLINICAL TRIAL	STEP 3: DESCRIBE REAL-WORLD DATA STUDY EMULATION OF ORIGINAL CLINICAL TRIAL		Data Source	
		3a. Minimal criteria for valid operationalization in real-world data source	3b. Criteria ranking with regard to uniqueness and importance		
OVERALL RATING				5	
GENERAL					
Sample size	Trial sample size	1.5x trial sample size ²	Must Have	Sample size among adult patients with metastatic breast cancer treated with first-line letrozole or letrozole + palbociclib ³	
Treated	444	666		1,148	5
Comparator	222	333		1,086	5
Length and frequency of follow-up ¹	Median reported follow-up: 23 months (range not reported)	Sufficient time coverage in dataset to identify outcome after receipt of treatment	Must Have	Earliest metastatic diagnosis date: Q3 1980 End of data cut: Q3 2023	Not Applicable⁴
VARIABLE-RELATED					

Variable	Trial criterion	Minimal criteria for valid operationalization in any real-world data source based on routine clinical care	Criteria ranking with regard to uniqueness and importance	Operationalization and coverage in data source	Rating
Treatment	125 mg of palbociclib per day, administered orally in 4-week cycles (3 weeks of treatment followed by 1 week off); 2.5 mg of letrozole per day, administered orally (continuous treatment)	Date of palbociclib and letrozole treatment	Must Have	Date of palbociclib and letrozole treatment is available. Lines of therapy are available.	5
Comparator	Placebo once per day, administered orally in 4-week cycles (3 weeks of treatment followed by 1 week off); 2.5 mg of letrozole per day, administered orally (continuous treatment)	Date of letrozole treatment	Must Have	Date of letrozole treatment is available. Lines of therapy are available.	5
Inclusion Criterion 1	Women, 18 years of age or older	Year of birth; sex	Must Have	Year of birth and sex are available.	5
Inclusion Criterion 2	Estrogen receptor-positive (ER+), human epidermal growth factor receptor 2-negative (HER2-) advanced breast cancer	Diagnosis of breast cancer; date of advanced/metastatic diagnosis; date and result of biomarker tests	Must Have	Breast cancer diagnosis, date of metastatic diagnosis, and dates and results of biomarker tests are available. Date of advanced diagnosis is not available.	4

Variable	Trial criterion	Minimal criteria for valid operationalization in any real-world data source based on routine clinical care	Criteria ranking with regard to uniqueness and importance	Operationalization and coverage in data source	Rating
Inclusion Criterion 3	No prior systemic therapy for advanced disease	Names/types and dates of antineoplastic treatment; date of advanced/metastatic diagnosis	Must Have	Dates of antineoplastic treatment are available. Lines of therapy are available.	5
Inclusion Criterion 4	Postmenopausal status: Prior bilateral oophorectomy, spontaneous cessation of menses for 12 consecutive months or more, or follicle-stimulating hormone and estradiol levels in postmenopausal ranges without an alternative cause	Diagnosis of menopause or related symptoms; curated post-menopausal status; date of last menstrual period	Nice to Have	Post-menopausal status is available.	5
Inclusion Criterion 5	Adequate organ function	Dates and results of laboratory tests for hematologic, hepatic, and renal function.	Nice to Have	Laboratory test results and dates are available.	5
Inclusion Criterion 6	ECOG performance status of 0 to 2	ECOG performance status result	Must Have	ECOG or Karnofsky performance status is available.	5
Inclusion Criterion 7	Measurable disease according to RECIST v1.1, or lesions only in the bone	RECIST assessment is not performed in routine care	Not Applicable	RECIST is not used to assess progression or response in a real-world setting. Progression will be assessed with available real-world information (see below).	Not Applicable

Variable	Trial criterion	Minimal criteria for valid operationalization in any real-world data source based on routine clinical care	Criteria ranking with regard to uniqueness and importance	Operationalization and coverage in data source	Rating
Exclusion Criterion 1	Prior adjuvant or neoadjuvant treatment with a nonsteroidal aromatase inhibitor was allowed unless disease had recurred while the patient was receiving the therapy or within 12 months after completing therapy	Date of surgery with curative intent; dates of antineoplastic treatment	Nice to Have	Dates of (neo)adjuvant and adjuvant treatment are available, but completeness could not be ascertained.	4
Exclusion Criterion 2	Advanced, symptomatic, visceral spread (i.e., spread to the viscera or main organs of the body) who were at risk for short-term, life-threatening complications	Life threatening complication in the short term is a qualitative assessment made by a physician and is not routinely available in medical records.	Not Applicable	Receipt of a study treatment will be assumed to indicate the clinician determined patient is not at risk of life-threatening complication in the short term. Per National Comprehensive Cancer Network (NCCN) guidelines, study treatments are not approved for palliative intent, but may be used in the real-world setting.	Not Applicable
Primary Outcome 1 (Definition & Ascertainment)	Progression-free survival	Date of death; curated progression variable; imaging results; dates of healthcare interactions	Must Have	Curated progression information is available. Date of death is available. Date of last activity is available.	4
Confounding Variable 1	Not applicable in a randomized setting	Age	Must Have	Year of birth is available.	5
Confounding Variable 2	Not applicable in a randomized setting	Sex	Must Have	Sex is available.	5
Confounding Variable 3	Not applicable in a randomized setting	Race/ethnicity	Must Have	Race/ethnicity is available.	5

Variable	Trial criterion	Minimal criteria for valid operationalization in any real-world data source based on routine clinical care	Criteria ranking with regard to uniqueness and importance	Operationalization and coverage in data source	Rating
Confounding Variable 4	Not applicable in a randomized setting	Performance status	Must Have	ECOG or Karnofsky performance status is available.	5
Confounding Variable 5	Not applicable in a randomized setting	Smoking status	Must Have	Smoking status is available.	5
Confounding Variable 6	Not applicable in a randomized setting	Progression/disease free-interval (Time from initial diagnosis to advanced/metastatic diagnosis)	Must Have	Date of initial and metastatic diagnosis are available. Date of advanced diagnosis is not available.	4
Confounding Variable 7	Not applicable in a randomized setting	Year of study treatment initiation	Must Have	Year of study treatment initiation is available.	5
Confounding Variable 8	Not applicable in a randomized setting	Number and/or location(s) of metastatic sites	Must Have	Metastatic site location is available. Number of metastatic sites can be determined.	5

Abbreviations: ECOG = Eastern Cooperative Oncology Group; ER+ = estrogen receptor positive; HER2- = human epidermal growth factor receptor 2-negative; NCCN = National Comprehensive Cancer Network; Q1/Q2/Q3/Q4 = quarter of year (Q1: January - March, Q2: April - June, Q3: July - September, Q4: October - December); RECIST = Response Evaluation Criteria in Solid Tumors.

Footnotes:

1. Follow-up time is stated as reported in the trial publication. Maximum available observation time is reported for the real-world data source. These are not directly comparable.
2. The minimum sample size for feasibility analyses was selected to account for expected attrition when all eligibility criteria are applied.
3. Sample sizes were calculated only among patients with metastatic breast cancer because curated dates of advanced breast cancer diagnosis are not available and line of therapy is defined relative to metastatic diagnosis in these data sources.
4. The final study period would be defined in the study protocol based on the date of treatment approval and relevant updates to treatment guidelines.

Keys for Ranking	
Scoring for Data Sources by Data Elements	
Scoring	Description
1	Data Requirements are not met
2	

3	Some data requirements are met
4	
5	All or nearly all data requirements are met

Appendix C: Code lists

Design Element	Variable	Code Type	Code
Inclusion	Non-adenocarcinoma histology	Diagnosis name	Intraductal carcinoma, non infiltrating, NOS Infiltrating duct mixed with other types of carcinoma (C50) Inflammatory carcinoma (C50) Comedocarcinoma, NOS (C50) Cribriform carcinoma, NOS Cribriform carcinoma in situ (C50) Papillary carcinoma, NOS Intraductal micropapillary carcinoma (C50) Comedocarcinoma, non infiltrating (C50) Paget disease, mammary (C50) Infiltrating lobular mixed with other types of carcinoma (C50) Neuroendocrine carcinoma, NOS Encapsulated papillary carcinoma with invasion (C50)
Inclusion	Bilateral surgical oophorectomy	Surgery name	Bilateral salpingo-oophorectomy with omentectomy, total abdominal hysterectomy and radical dissection for debulking Bilateral salpingo-oophorectomy with omentectomy, total abdominal hysterectomy and radical dissection for debulking; with pelvic lymphadenectomy and limited para-aortic lymphadenectomy Bilateral salpingo-oophorectomy with total omentectomy, total abdominal hysterectomy for malignancy Total abdominal hysterectomy with bilateral salpingo-oophorectomy Resection (initial) of ovarian, tubal or primary peritoneal malignancy with bilateral salpingo-oophorectomy and omentectomy; with radical dissection for debulking (ie, radical excision or destruction, intra-abdominal or retroperitoneal tumors) Resection (initial) of ovarian, tubal or primary peritoneal malignancy with bilateral salpingo-oophorectomy and omentectomy; with total abdominal hysterectomy, pelvic and limited para-aortic lymphadenectomy Laparoscopic bilateral salpingo-oophorectomy
Inclusion	Absolute neutrophil count (ANC)	Lab test name	Neutrophils [# /volume] in Blood Neutrophils [# /volume] in Blood by Automated count Neutrophils [# /volume] in Blood by Manual count
		Unit	x10 ⁽³⁾ /mCL cells/uL 10*9 cells/L

Design Element	Variable	Code Type	Code
			10*9/L
Inclusion	Platelets	Lab test name	Platelets [# /volume] in Blood Platelets [# /volume] in Blood by Automated count Platelets [# /volume] in Blood by Estimate Platelets [# /volume] in Blood by Manual count
		Unit	10*9 cells/L x10(3)/mcL
Inclusion	Hemoglobin	Lab test name	Hemoglobin [Mass/volume] in Blood Hemoglobin [Mass/volume] in Blood by calculation Hemoglobin [Mass/volume] in Arterial blood Hemoglobin [Mass/volume] in Venous blood
		Unit	g/dL
Inclusion	Creatinine clearance	Lab test name	Creatinine [Mass/volume] in Blood Creatinine [Mass/volume] in Serum or Plasma
		Unit	mg/dL
Inclusion	Serum total bilirubin	Lab test name	Bilirubin.total [Mass/volume] in Serum or Plasma Bilirubin.total [Mass/volume] in Blood
		Unit	mg/dL
Inclusion	Gilbert's disease	ICD-10 code	E80.4
Inclusion	AST (SGOT)	Lab test name	Aspartate aminotransferase [Enzymatic activity/volume] in Serum or Plasma Aspartate aminotransferase [Enzymatic activity/volume] in Serum or Plasma by With P-5'-P
		Unit	U/L IU/L
Inclusion	ALT (SGPT)	Lab test name	Alanine aminotransferase [Enzymatic activity/volume] in Blood Alanine aminotransferase [Enzymatic activity/volume] in Serum or Plasma by With P-5'-P Alanine aminotransferase [Enzymatic activity/volume] in Serum or Plasma by No addition of P-5'-P Alanine aminotransferase [Enzymatic activity/volume] in Serum or Plasma
		Unit	U/L IU/L
Inclusion	Alkaline phosphatase	Lab test name	Alkaline phosphatase [Enzymatic activity/volume] in Serum or Plasma Alkaline phosphatase [Enzymatic activity/volume] in Blood
		Unit	U/L

Design Element	Variable	Code Type	Code
			IU/L
Exclusion	CYP3A4 inhibitors	Generic name	Amprenavir Atazanavir Boceprevir Clarithromycin Conivaptan Delavirdine Diltiazem Erythromycin Fosamprenavir Indinavir Itraconazole Ketoconazole Lopinavir Mibefradil Miconazole Nefazodone Nelfinavir Posaconazole Ritonavir Saquinavir Telaprevir Telithromycin Verapamil Voriconazole
Exclusion	Major surgery	Surgery name	Modified radical mastectomy Partial mastectomy Partial mastectomy with axillary lymphadenectomy Simple mastectomy Prophylactic mastectomy Excision of internal mammary lymph nodes Excision of sentinel lymph node Radical mastectomy Subcutaneous mastectomy Total mastectomy and axillary clearance Hysterectomy Ligation of fallopian tube Simple mastectomy with axillary lymph node sampling

Design Element	Variable	Code Type	Code
Exclusion	Long or short QT syndrome ²⁶	ICD-10 code	I45.8
Exclusion	Brugada syndrome ²⁷	ICD-10 code	I49.8
Exclusion	Torsade de Pointes (TdP)	ICD-10 code	I47.21
Exclusion	Hypocalcemia ²⁸	ICD-10 code	E83.51
Exclusion	Hypokalemia ²⁹	ICD-10 code	E87.6
Exclusion	Hypomagnesemia ³⁰	ICD-10 code	E83.42
Exclusion	Myocardial infarction	ICD-10 code	I21 I22 I25.2
Exclusion	Severe/unstable angina	ICD-10 code	I20.0
Exclusion	Cardiac dysrhythmias ³¹	ICD-10 code	I47.0 I47.1 I47.2 I47.9 I48.0 I48.1 I48.2 I48.3 I48.4 I48.91 I48.92 I49.1 I49.2 I49.3 I49.40 I49.49 I49.5 I49.8 I49.9 R00.0 R00.1 R00.2
Exclusion	Atrial fibrillation ³²	ICD-10 code	I48
Exclusion	Symptomatic congestive heart failure ³³	ICD-10 code	I50.9
Exclusion	Cerebrovascular accident ³⁴	ICD-10 code	I60 I61

Design Element	Variable	Code Type	Code
			I62 I63 H34.1 G45
Exclusion	Symptomatic pulmonary embolism ³⁵	ICD-10 code	I26
Exclusion	Inflammatory bowel disease or chronic diarrhea ³⁶	ICD-10 code	K50
Exclusion	Inflammatory bowel disease or chronic diarrhea	ICD-10 code	K51
Exclusion	Short bowel syndrome	ICD-10 code	K90.82
Exclusion	Human immunodeficiency virus infection ³⁷	SNOMED code	91947003 445945000
Covariate	Disease site: visceral	Diagnosis name	Metastatic malignant neoplasm to liver Metastatic malignant neoplasm to left lung Metastatic malignant neoplasm to pleura Metastatic malignant neoplasm to lung Metastatic malignant neoplasm to right lung Metastatic malignant neoplasm to respiratory tract
Covariate	Prior adjuvant or neoadjuvant chemotherapy	Therapy name	Capecitabine Carboplatin Cyclophosphamide Docetaxel Doxorubicin Epirubicin Etoposide Fluorouracil Gemcitabine Methotrexate Oxaliplatin Paclitaxel Pemetrexed
Covariate	Prior adjuvant hormone	Therapy name	Anastrozole Exemestane Fulvestrant Goserelin Letrozole

Design Element	Variable	Code Type	Code
			Leuprolide Megestrol Tamoxifen Toremifene Triptorelin
